  - K25.5 Chronic or unspecified gastric ulcer with perforation

- K26.2 Acute duodenal ulcer with both hemorrhage and perforation
- K26.4 Chronic or unspecified duodenal ulcer with hemorrhage
- K26.6 Chronic or unspecified duodenal ulcer with both hemorrhage and perforation
- K27.4 Chronic or unspecified peptic ulcer, site unspecified, with hemorrhage
- K27.5 Chronic or unspecified peptic ulcer, site unspecified, with perforation
- K27.6 Chronic or unspecified peptic ulcer, site unspecified, with both hemorrhage and perforation
- K28.1 Acute gastroieiunal ulcer with perforation
- K28.2 Acute gastrojejunal ulcer with both hemorrhage and perforation
- K29.31 Chronic superficial gastritis with bleeding
- K29.91 Gastroduodenitis, unspecified, with bleeding
- K57.11 Diverticulosis of small intestine without perforation or abscess with bleeding
- K57.21 Diverticulitis of large intestine with perforation and abscess with bleeding
- K57.51 Diverticulosis of both small and large intestine without perforation or abscess with bleeding
- K57.53 Diverticulitis of both small and large intestine without perforation or abscess with bleeding
- K57.93 Diverticulitis of intestine, part unspecified, without perforation or abscess with bleeding
- K62.5 Hemorrhage of anus and rectum
- K64.1 Second degree hemorrhoids
- K64.3 Fourth degree hemorrhoids
- K64.9 Unspecified hemorrhoids
- K92.0 Hematemesis
- K92.1 Melena
- N89.7 Hematocolpos
- N92.1 Excessive and frequent menstruation with irregular cycle
- N93.8 Other specified abnormal uterine and vaginal bleeding
- R04.0 Epistaxis
- R31.0 Gross hematuria
- R31.9 Hematuria, unspecified
- R58 Hemorrhage, not elsewhere classified
- 185.01 Esophageal varices with bleeding
- K22.6 Gastro-esophageal laceration-hemorrhage syndrome
- K25.0 Acute gastric ulcer with hemorrhage
- K25.6 Chronic or unspecified gastric ulcer with both hemorrhage and perforation
- K26.0 Acute duodenal ulcer with hemorrhage
- K26.1 Acute duodenal ulcer with perforation
- K26.5 Chronic or unspecified duodenal ulcer with perforation
- K27.0 Acute peptic ulcer, site unspecified, with hemorrhage
- K27.1 Acute peptic ulcer, site unspecified, with perforation
- K27.2 Acute peptic ulcer, site unspecified, with both hemorrhage and perforation
- K28.0 Acute gastroieiunal ulcer with hemorrhage
- K28.4 Chronic or unspecified gastrolejunal ulcer with hemorrhage
- K28.5 Chronic or unspecified gastroleiunal ulcer with perforation
- K28.6 Chronic or unspecified gastrojejunal ulcer with both hemorrhage and perforation
- K29.01 Acute gastritis with bleeding
- K29.21 Alcoholic gastritis with bleeding
- K29.41 Chronic atrophic gastritis with bleeding
- K29.51 Unspecified chronic gastritis with bleeding
- K29.61 Other gastritis with bleeding
- K29.71 Gastritis, unspecified, with bleeding
- K29.81 Duodenitis with bleeding
- K31.811
- Angiodysplasia of stomach and duodenum with bleeding
- K55.21 Angiodysplasia of colon with hemorrhage
- K57.01 Diverticulitis of small intestine with perforation and abscess with bleeding
- K57.31 Diverticulosis of large intestine without perforation or abscess with bleeding
- K57.41 Diverticulitis of both small and large intestine with perforation and abscess with bleeding
- K57.81 Diverticulitis of intestine, part unspecified, with perforation and abscess with bleeding
- K57.91 Diverticulosis of intestine, part unspecified, without perforation or abscess with bleeding
- K64.0 First degree hemorrhoids
- K64.2 Third degree hemorrhoids
- K64.4 Residual hemorrhoidal skin tags
- K64.5 Perianal venous thrombosis
| K64.8 | 3 | Other hemorrhoids                                   |
|-------|---|---|
| K92.2 | 2 | Gastrointestinal hemorrhage, unspecified            |
| N89.8 |   | Other specified noninflammatory disorders of vagina |
| N93.9 | ) | Abnormal uterine and vaginal bleeding, unspecified  |
| R04.1 |   | Hemorrhage from throat                              |
| R04.2 | 2 | Hemoptysis  |

Ξ.

Inpatient, Any Diagnosis: ICD-9 Codes 280.0 - IRON DEFICIENCY ANEMIA SECONDARY TO BLOOD LOSS (CHRONIC) 455.7 - UNSPECIFIED THROMBOSED HEMORRHOIDS 459.0 - HEMORRHAGE UNSPECIFIED 530.10 - ESOPHAGITIS UNSPECIFIED 530.13 - EOSINOPHILIC ESOPHAGITIS 531.0 - ACUTE GASTRIC ULCER WITH HEMORRHAGE 531.1 - ACUTE GASTRIC UI CER WITH PERFORATION 531.2 - ACUTE GASTRIC ULCER WITH HEMORRHAGE AND PERFORATION 531.20 - ACUTE GASTRIC ULCER WITH HEMORRHAGE AND PERFORATION WITHOUT OBSTRUCTION 531.3 - ACUTE GASTRIC ULCER WITHOUT MENTION OF HEMORRHAGE OR PERFORATION 531.4 - CHRONIC OR UNSPECIFIED GASTRIC ULCER WITH HEMORRHAGE 531.6 - CHRONIC OR UNSPECIFIED GASTRIC ULCER WITH HEMORRHAGE AND PERFORATION 531.61 - CHRONIC OR UNSPECIFIED GASTRIC ULCER WITH HEMORRHAGE AND PERFORATION WITH OBSTRUCTION 531.9 - GASTRIC ULCER UNSPECIFIED AS ACUTE OR CHRONIC WITHOUT MENTION OF HEMORRHAGE OR PERFORATION 532.0 - ACUTE DUODENAL ULCER WITH HEMORRHAGE 532.00 - ACUTE DUODENAL ULCER WITH HEMORRHAGE WITHOUT OBSTRUCTION 532.01 - ACUTE DUODENAL ULCER WITH HEMORRHAGE WITH OBSTRUCTION 532.2 - ACUTE DUODENAL ULCER WITH HEMORRHAGE AND PERFORATION 532.20 - ACUTE DUODENAL ULCER WITH HEMORRHAGE AND PERFORATION WITHOUT OBSTRUCTION 532.3 - ACUTE DUODENAL ULCER WITHOUT MENTION OF HEMORRHAGE OR PERFORATION 532.4 - CHRONIC OR UNSPECIFIED DUODENAL ULCER WITH HEMORRHAGE 532.41 - CHRONIC OR UNSPECIFIED DUODENAL ULCER WITH HEMORRHAGE WITH OBSTRUCTION 532.5 - CHRONIC OR UNSPECIFIED DUODENAL ULCER WITH PERFORATION 532.61 - CHRONIC OR UNSPECIFIED DUODENAL ULCER WITH HEMORRHAGE AND PERFORATION WITH OBSTRUCTION 533.0 - ACUTE PEPTIC ULCER OF UNSPECIFIED SITE WITH HEMORRHAGE 533.00 - ACUTE PEPTIC ULCER OF UNSPECIFIED SITE WITH HEMORRHAGE WITHOUT OBSTRUCTION 533.01 - ACUTE PEPTIC ULCER OF UNSPECIFIED SITE WITH HEMORRHAGE WITH OBSTRUCTION 533.1 - ACUTE PEPTIC ULCER OF UNSPECIFIED SITE WITH PERFORATION 533.2 - ACUTE PEPTIC ULCER OF UNSPECIFIED SITE WITH HEMORRHAGE AND PERFORATION 533.20 - ACUTE PEPTIC ULCER OF UNSPECIFIED SITE WITH HEMORRHAGE AND PERFORATION WITHOUT OBSTRUCTION 533.3 - ACUTE PEPTIC ULCER OF UNSPECIFIED SITE WITHOUT MENTION OF HEMORRHAGE AND PERFORATION 533.6 - CHRONIC OR UNSPECIFIED PEPTIC ULCER OF UNSPECIFIED SITE WITH HEMORRHAGE AND PERFORATION 533.60 - CHRONIC OR UNSPECIFIED PEPTIC ULCER OF UNSPECIFIED SITE WITH HEMORRHAGE AND PERFORATION WITHOUT OBSTRUCTION 533.7 - CHRONIC PEPTIC ULCER OF UNSPECIFIED SITE WITHOUT MENTION OF HEMORRHAGE OR PERFORATION 534.00 - ACUTE GASTROJEJUNAL ULCER WITH HEMORRHAGE WITHOUT OBSTRUCTION 534.01 - ACUTE GASTROJEJUNAL ULCER WITH HEMORRHAGE WITH OBSTRUCTION 534.20 - ACUTE GASTROJEJUNAL ULCER WITH HEMORRHAGE AND PERFORATION WITHOUT OBSTRUCTION 534.3 - ACUTE GASTROJEJUNAL ULCER WITHOUT MENTION OF HEMORRHAGE OR PERFORATION 534.40 - CHRONIC OR UNSPECIFIED GASTROJEJUNAL ULCER WITH HEMORRHAGE WITHOUT OBSTRUCTION 534.41 - CHRONIC OR UNSPECIFIED GASTROJEJUNAL ULCER WITH HEMORRHAGE WITH OBSTRUCTION 534.61 - CHRONIC OR UNSPECIFIED GASTROJEJUNAL ULCER WITH HEMORRHAGE AND PERFORATION WITH OBSTRUCTION 534.7 - CHRONIC GASTROJEJUNAL ULCER WITHOUT MENTION OF HEMORRHAGE OR PERFORATION 534.9 - GASTROJEJUNAL ULCER UNSPECIFIED AS ACUTE OR CHRONIC WITHOUT MENTION OF HEMORRHAGE OR PERFORATION 535.00 - ACUTE GASTRITIS (WITHOUT HEMORRHAGE) 535.01 - ACUTE GASTRITIS WITH HEMORRHAGE 535.10 - ATROPHIC GASTRITIS (WITHOUT HEMORRHAGE) 535.20 - GASTRIC MUCOSAL HYPERTROPHY (WITHOUT HEMORRHAGE)

535.21 - GASTRIC MUCOSAL HYPERTROPHY WITH HEMORRHAGE 535.31 - ALCOHOLIC GASTRITIS WITH HEMORRHAGE 535.40 - OTHER SPECIFIED GASTRITIS (WITHOUT HEMORRHAGE) 535.41 - OTHER SPECIFIED GASTRITIS WITH HEMORRHAGE 562.00 - DIVERTICULOSIS OF SMALL INTESTINE (WITHOUT HEMORRHAGE) 562.01 - DIVERTICULITIS OF SMALL INTESTINE (WITHOUT HEMORRHAGE) 562.03 - DIVERTICULITIS OF SMALL INTESTINE WITH HEMORRHAGE 562.11 - DIVERTICULITIS OF COLON (WITHOUT HEMORRHAGE) 562.13 - DIVERTICULITIS OF COLON WITH HEMORRHAGE 569.85 - ANGIODYSPLASIA OF INTESTINE WITH HEMORRHAGE 578.0 - HEMATEMESIS 578.1 - BLOOD IN STOOL 578.9 - HEMORRHAGE OF GASTROINTESTINAL TRACT UNSPECIFIED 593.81 - VASCULAR DISORDERS OF KIDNEY 599.70 - HEMATURIA UNSPECIFIED 599.71 - GROSS HEMATURIA 623.6 - VAGINAL HEMATOMA 626.6 - METRORRHAGIA 784.7 - FPISTAXIS 784.8 - HEMORRHAGE FROM THROAT 786.31 - ACUTE IDIOPATHIC PULMONARY HEMORRHAGE IN INFANTS 285.1 - ACUTE POSTHEMORRHAGIC ANEMIA 455.1 - INTERNAL THROMBOSED HEMORRHOIDS 455.2 - INTERNAL HEMORRHOIDS WITH OTHER COMPLICATION 455.4 - EXTERNAL THROMBOSED HEMORRHOIDS 455.5 - EXTERNAL HEMORRHOIDS WITH OTHER COMPLICATION 455.6 - UNSPECIFIED HEMORRHOIDS WITHOUT COMPLICATION 455.8 - UNSPECIFIED HEMORRHOIDS WITH OTHER COMPLICATION 455.9 - RESIDUAL HEMORRHOIDAL SKIN TAGS 456.0 - ESOPHAGEAL VARICES WITH BLEEDING 456.20 - ESOPHAGEAL VARICES IN DISEASES CLASSIFIED ELSEWHERE WITH BLEEDING 530.1 - ESOPHAGITIS 530.11 - REFLUX ESOPHAGITIS 530.12 - ACUTE ESOPHAGITIS 530.19 - OTHER ESOPHAGITIS 530.7 - GASTROESOPHAGEAL LACERATION-HEMORRHAGE SYNDROME 530.82 - ESOPHAGEAL HEMORRHAGE 531.00 - ACUTE GASTRIC ULCER WITH HEMORRHAGE WITHOUT OBSTRUCTION 531.01 - ACUTE GASTRIC ULCER WITH HEMORRHAGE WITH OBSTRUCTION 531.21 - ACUTE GASTRIC ULCER WITH HEMORRHAGE AND PERFORATION WITH OBSTRUCTION 531.40 - CHRONIC OR UNSPECIFIED GASTRIC ULCER WITH HEMORRHAGE WITHOUT OBSTRUCTION 531.41 - CHRONIC OR UNSPECIFIED GASTRIC ULCER WITH HEMORRHAGE WITH OBSTRUCTION 531.5 - CHRONIC OR UNSPECIFIED GASTRIC ULCER WITH PERFORATION 531.60 - CHRONIC OR UNSPECIFIED GASTRIC ULCER WITH HEMORRHAGE AND PERFORATION WITHOUT OBSTRUCTION 531.7 - CHRONIC GASTRIC ULCER WITHOUT MENTION OF HEMORRHAGE OR PERFORATION 532.1 - ACUTE DUODENAL ULCER WITH PERFORATION 532.21 - ACUTE DUODENAL ULCER WITH HEMORRHAGE AND PERFORATION WITH OBSTRUCTION 532.40 - CHRONIC OR UNSPECIFIED DUODENAL ULCER WITH HEMORRHAGE WITHOUT OBSTRUCTION

532.6 - CHRONIC OR UNSPECIFIED DUODENAL ULCER WITH HEMORRHAGE AND PERFORATION 532.60 - CHRONIC OR UNSPECIFIED DUODENAL ULCER WITH HEMORRHAGE AND PERFORATION WITHOUT OBSTRUCTION 532.7 - CHRONIC DUODENAL ULCER WITHOUT MENTION OF HEMORRHAGE OR PERFORATION 532.9 - DUODENAL ULCER UNSPECIFIED AS ACUTE OR CHRONIC WITHOUT MENTION OF HEMORRHAGE OR PERFORATION 533.21 - ACUTE PEPTIC ULCER OF UNSPECIFIED SITE WITH HEMORRHAGE AND PERFORATION WITH OBSTRUCTION 533.4 - CHRONIC OR UNSPECIFIED PEPTIC ULCER OF UNSPECIFIED SITE WITH HEMORRHAGE 533.40 - CHRONIC OR UNSPECIFIED PEPTIC ULCER OF UNSPECIFIED SITE WITH HEMORRHAGE WITHOUT OBSTRUCTION 533.41 - CHRONIC OR UNSPECIFIED PEPTIC ULCER OF UNSPECIFIED SITE WITH HEMORRHAGE WITH OBSTRUCTION 533.5 - CHRONIC OR UNSPECIFIED PEPTIC ULCER OF UNSPECIFIED SITE WITH PERFORATION 533.61 - CHRONIC OR UNSPECIFIED PEPTIC ULCER OF UNSPECIFIED SITE WITH HEMORRHAGE AND PERFORATION WITH OBSTRUCTION 533.9 - PEPTIC ULCER OF UNSPECIFIED SITE UNSPECIFIED AS ACUTE OR CHRONIC WITHOUT MENTION OF HEMORRHAGE OR PERFORATION 534.0 - ACUTE GASTROJEJUNAL ULCER WITH HEMORRHAGE 534.1 - ACUTE GASTROJEJUNAL ULCER WITH PERFORATION 534.2 - ACUTE GASTROJEJUNAL ULCER WITH HEMORRHAGE AND PERFORATION 534,21 - ACUTE GASTROJEJUNAL ULCER WITH HEMORRHAGE AND PERFORATION WITH OBSTRUCTION 534.4 - CHRONIC OR UNSPECIFIED GASTROJEJUNAL ULCER WITH HEMORRHAGE 534.5 - CHRONIC OR UNSPECIFIED GASTROJEJUNAL ULCER WITH PERFORATION 534.6 - CHRONIC OR UNSPECIFIED GASTROJEJUNAL ULCER WITH HEMORRHAGE AND PERFORATION 534.60 - CHRONIC OR UNSPECIFIED GASTROJEJUNAL ULCER WITH HEMORRHAGE AND PERFORATION WITHOUT OBSTRUCTION 535.11 - ATROPHIC GASTRITIS WITH HEMORRHAGE 535.30 - ALCOHOLIC GASTRITIS (WITHOUT HEMORRHAGE) 535.50 - UNSPECIFIED GASTRITIS AND GASTRODUODENITIS (WITHOUT HEMORRHAGE) 535.51 - UNSPECIFIED GASTRITIS AND GASTRODUODENITIS WITH HEMORRHAGE 535.60 - DUODENITIS (WITHOUT HEMORRHAGE) 535.61 - DUODENITIS WITH HEMORRHAGE 537.83 - ANGIODYSPLASIA OF STOMACH AND DUODENUM WITH HEMORRHAGE 562.02 - DIVERTICULOSIS OF SMALL INTESTINE WITH HEMORRHAGE 562.10 - DIVERTICULOSIS OF COLON (WITHOUT HEMORRHAGE) 562.12 - DIVERTICULOSIS OF COLON WITH HEMORRHAGE 569.3 - HEMORRHAGE OF RECTUM AND ANUS 623.8 - OTHER SPECIFIED NONINFLAMMATORY DISORDERS OF VAGINA 626.8 - OTHER DISORDERS OF MENSTRUATION AND OTHER ABNORMAL BLEEDING FROM FEMALE GENITAL TRACT 786.3 - HEMOPTYSIS 786.30 - HEMOPTYSIS UNSPECIFIED 786.39 - OTHER HEMOPTYSIS 285.9 - ANEMIA UNSPECIFIED 790.92 - ABNORMAL COAGULATION PROFILE 363.63 - CHOROIDAL RUPTURE 626.2 - EXCESSIVE OR FREQUENT MENSTRUATION 372.72 - CONJUNCTIVAL HEMORRHAGE

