#### 1.3 Primary endpoint for replication

Time from randomization to the first confirmed, adjudicated occurrence of a major bleeding or clinically relevant non-major bleeding event up to 365 days after initiating anticoagulation treatment.

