#### 6.3 Outcome variables and study follow-up:

6.3.1 Outcome variables

Safety outcome variables of interest (definitions provided in **Appendix**):

- Primary outcome: Major bleeding and clinically relevant non-major bleeding through 365 days of treatment with apixaban or rivaroxaban.
- Secondary outcomes:
  - To assess the frequency of major bleeding events and clinically relevant non-major bleeding individually
  - $\circ$   $\,$  To assess the frequency of intracranial and extracranial bleeding events
  - o Stroke
  - $\circ$  All-cause mortality

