Heparin Sodium Porcine/Dextrose (5% in water or 5% in water/PF), Heparin Sodium, Program Sodium Porcine, and Warfarin Sodium	
2       Creatine clearance < 15 ml/min calculated with the Cockcroft-Gault formula	
Any contradiction for anticoagulation with apixaban or rivaroxaban as determined by the treating physician such as, but not limited to one of the following:	
Mesaured [-180, 0] in any diagnosis position and in an inpatient setting (transfusion codes required for non-critical sites)	
Maior Bleeding See "Major Bleeding" Sheet	
Active Bleeding     Measured [-180,0] in any diagnosis position in an inpatient setting (transfusion codes not required for non-critical sites)     Clinically Relevant Non-Major Bleeding Events	
See "CRNM Bleeds Sheet"	
Measuered [-180, 0] in any diagnosis position in an inpatient or oupatient setting:           DVT           ICD-9 Diagnosis: 451.1x, 451.2x, 451.81, 451.9x, 453.1x, 453.2x, 453.8x, 453.9x, 453.40, 453.41, 453.42, 453.0           ICD-10 Diagnosis: 180.1x, 180.2, 180.3, 180.9, 182.0, 182.1, 182.2x (except 182.21), 182.4x, 182.6x, 182.80, 182.90, 181.A1x, 182.E1x, 182.C1x	
2) Other Indication for anticoagulation (e.g. mechanical valves, venous thromosis)       PE         ICD-9 Diagnosis:       415.1, 415.10, 415.11, 415.12, 415.13, 415.5, 415.16, 417.17, 415.19, 41	
Prosthetic Heart Valve ICD-9 Diagnosis: V43.3 ICD-10 Diagnosis: Z95.2	

1

	Measured [-180, 0] in prescription claims	
3) Dual Antiplatelet Use	Use of Antiplaelets Any of the following: cilostazol, dipyridamole, ticlopidine HCl, aspirin, clopidogrel bisulfate, prasugrel HCl, ticagerlor, aspirin/dipyridamole, ezetimibe	

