- K92.2 Gastrointestinal hemorrhage, unspecified
- N89.7 Hematocolpos
- N93.8 Other specified abnormal uterine and vaginal bleeding
- R04.2 Hemoptysis
- R31.0 Gross hematuria
- K20 Esophagitis
- K20.9 Esophagitis, unspecified
- K21.0 Gastro-esophageal reflux disease with esophagitis
- K25.6 Chronic or unspecified gastric ulcer with both hemorrhage and perforation
- K26.0 Acute duodenal ulcer with hemorrhage
- K26.5 Chronic or unspecified duodenal ulcer with perforation
- K26.6 Chronic or unspecified duodenal ulcer with both hemorrhage and perforation
- K27.0 Acute peptic ulcer, site unspecified, with hemorrhage

- K27.4 Chronic or unspecified peptic ulcer, site unspecified, with hemorrhage
- K28.1 Acute gastrojejunal ulcer with perforation
- K28.2 Acute gastrojejunal ulcer with both hemorrhage and perforation
- K28.5 Chronic or unspecified gastrojejunal ulcer with perforation
- K29.21 Alcoholic gastritis with bleeding
- K29.61 Other gastritis with bleeding
- K29.81 Duodenitis with bleeding
- K29.91 Gastroduodenitis, unspecified, with bleeding
- K31.811 Angiodysplasia of stomach and duodenum with bleeding
- K55.21 Angiodysplasia of colon with hemorrhage
- K57.01 Diverticulitis of small intestine with perforation and abscess with bleeding
- K57.31 Diverticulosis of large intestine without perforation or abscess with bleeding
- K57.53 Diverticulitis of both small and large intestine without perforation or abscess with bleeding
- K64.1 Second degree hemorrhoids
- K64.2 Third degree hemorrhoids
- K64.3 Fourth degree hemorrhoids
- K64.4 Residual hemorrhoidal skin tags
- K92.1 Melena
- N89.8 Other specified noninflammatory disorders of vagina
- N93.9 Abnormal uterine and vaginal bleeding, unspecified
- R04.0 Epistaxis
- R04.1 Hemorrhage from throat
- R58 Hemorrhage, not elsewhere classified
- D64.9 Anemia, unspecified
- R79.1 Abnormal coagulation profile
- H11.30 Conjunctival hemorrhage, unspecified eye
- H11.31 Conjunctival hemorrhage, right eye
- H11.32 Conjunctival hemorrhage, left eye
- H11.33 Conjunctival hemorrhage, bilateral
- H31.321 Choroidal rupture, right eye
- H31.322 Choroidal rupture, left eye
- H31.323 Choroidal rupture, bilateral
- H31.329 Choroidal rupture, unspecified eye
- N92.1 Excessive and frequent menstruation with irregular cycle
- R31.1 Benign essential microscopic hematuria
- R31.2 Other microscopic hematuria
- R31.29 Other microscopic hematuria
- N92.0 Excessive and frequent menstruation with regular cycle

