- R31.21 Asymptomatic microscopic hematuria
- R31.9 Hematuria, unspecified

Procedure	Codes Description	

- CPT-4 codes
- 1960 Anesthesia for vaginal delivery only
- 1961 Anesthesia for cesarean delivery only
- 1962 Anesthesia for urgent hysterectomy following delivery
- 1963 Anesthesia for cesarean hysterectomy w/o any labor analgesia/anesthesia care
- 1967 Neuraxial labor analgesia/anesthesia, planned vaginal delivery
- 1968 Anesthesia for cesarean delivery following neuraxial labor analgesia/anesthesia
- 1969 Anes for cesarean hysterectomy following neuraxial labor analgesia/anesthesia
- 59050 Fetal monitoring in labor, physician w/written report; s & i
- 59051 Fetal monitoring in labor, physician w/written report; intrepretation only
- 59400 ROUTINE TOTAL OBSTETRIC CARE including antepartum care, vaginal delivery (with or without episiotomy, and/or forceps) and postpartum care.
- 59409 Vaginal delivery only (w/wo episiotomy &/or forceps)
- 59410 Vaginal delivery only (w/wo episiotomy &/or forceps); w/postpartum care
- 59412 Ext cephalic version, w/wo tocolysis
- 59414 Delivery of placenta (separate proc)
- 59430 Postpartum care only
- 59510 Routine obstetric care w/antepartum care, cesarean delivery, & postpartum care
- 59514 Cesarean delivery only
- 59515 Cesarean delivery only; w/postpartum care
- 59525 Subtotal/total hysterectomy after cesarean delivery
- 59610 Routine obstetric care including antepartum care, vaginal delivery (with or without episiotomy, and/or forceps) and postpartum care, after previous cesarean delivery
- 59612 Vaginal delivery only, after previous cesarean delivery (with or without episiotomy and/or forceps)
- 59614 Vaginal delivery only, previous cesarean delivery w/postpartum care
- 59618 Routine obstetric care including antepartum care, cesarean delivery, and postpartum care, following attempted vaginal delivery after previous cesarean delivery
- 59620 Cesarean delivery after failed vaginal delivery, previous cesarean delivery
- 59622 Cesarean delivery after failed vaginal delivery, previous cesarean delivery; w/postpartum care
- 99436 Attendance at delivery, at request of delivering physician, & stabilization of newborn
- 99440 Newborn resuscitation

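### Both code lists for clinically relevant non-major bleeding include codes that name no bleed, so the primary outcome is non-specific and the hazard ratio may be diluted by an unknown amount

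*Combined protocol and SAP*

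**What the plan says.** Section 6.3.1 defines the outcome: "Primary outcome: Major bleeding and clinically relevant non-major bleeding through 365 days of treatment with apixaban or rivaroxaban". The endpoint being emulated (section 1.3) is "Time from randomization to the first confirmed, adjudicated occurrence of a major bleeding or clinically relevant non-major bleeding event".

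The outcome row of Appendix A counts a CRNM event from one listed code "in any diagnosis position in an inpatient setting (transfusion codes not required for non-critical sites". The code lists are the two headed Inpatient, Any Diagnosis, one for ICD-9 and one for ICD-10. They do not carry the CRNM sheet name in the published text. I identify them by that heading and by the absence of the transfusion block found in the major-bleeding lists.

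The ICD-9 list includes "285.9 - ANEMIA UNSPECIFIED 790.92 - ABNORMAL COAGULATION PROFILE" and "530.11 - REFLUX ESOPHAGITIS". The ICD-10 list includes "D64.9 Anemia, unspecified", "K21.0 Gastro-esophageal reflux disease with esophagitis" and "R31.21 Asymptomatic microscopic hematuria".

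The Active Bleeding exclusion in Appendix A uses the same CRNM sheet, together with the major-bleeding sheet, over days -180 to 0. Section 6.3.2 ends follow-up at the first outcome. Section 13.2, for sensitivity analyses, is blank.

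**The concern.** A patient admitted for another reason who carries a secondary code for unspecified anemia or reflux esophagitis becomes a primary-outcome event. That patient leaves follow-up on that day, so any later real bleed is not seen. Nothing in the plan requires an accompanying bleeding code, a primary diagnosis position or adjudication.

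The study exists to reproduce a trial result, so bias in the hazard ratio matters more here than power. If events unrelated to the drug are mixed into the outcome, a real difference between apixaban and rivaroxaban shrinks, and a very large sample puts a tight interval around the shrunken value. The same list also removes some patients at baseline as active bleeders although they had no bleed.

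**Working it through.** **1. Codes whose label names no bleed (Appendix A, Inpatient, Any Diagnosis lists).**

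| Group | ICD-9 | ICD-10 |
|---|---|---|
| Unspecified anemia; abnormal coagulation profile | 285.9, 790.92 (2) | D64.9, R79.1 (2) |
| Esophagitis | 530.1, .10, .11, .12, .13, .19 (6) | K20, K20.0, .8, .9, K21.0 (5) |
| Hemorrhoids, skin tags | 455.1, .4, .6, .7, .9 (5) | K64.0-.5, .8, .9 (8) |
| Ulcer, perforation only | 531.1, 531.5, 532.1, 532.5, 533.1, 533.5, 534.1, 534.5 (8) | K25.1, K25.5, K26.1, K26.5, K27.1, K27.5, K28.1, K28.5 (8) |
| Choroidal rupture | 363.63 (1) | H31.321, .322, .323, .329 (4) |
| Renal vascular or vaginal disorder | 593.81, 623.8 (2) | N89.8 (1) |
| Total | 24 | 28 |

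The counts leave out three groups: the ICD-9 labels that state there is no hemorrhage, which are a separate matter; 455.2, 455.5 and 455.8 (hemorrhoids with an unnamed complication); and microscopic hematuria.

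**2. Is there a safeguard elsewhere?** The major-bleeding lists repeat the esophagitis, hemorrhoid, perforation, 593.81 and 623.8/N89.8 codes, but in a block that needs a transfusion code. The CRNM lists drop that condition. They also add 285.9/D64.9, 790.92/R79.1 and 363.63/H31.32x, which are not on the major lists.

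**3. The plan's own figures (section 10).** Events = matched patients x risk. Pooled: 368,214 x 41.4155034/1,000 = 15,249.77, as stated. Optum: 68,134 x 19.8838767/1,000 = 1,354.77, as stated. Power (Schoenfeld, 1:1, two-sided 0.05) = Φ(|ln HR| x √D/2 - 1.96). For Optum at HR 0.8: 0.2231 x 18.40 - 1.96 = 2.147, so power is 0.9841, as stated.

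**4. Dilution.** Let f be the share of comparator events that are non-bleeds. The documents do not give f, so the values below are assumptions. Then

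HR observed = (1 - f) x HR true + f x HR non-bleed.

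The 95% interval uses SE(log HR) ≈ 2/√15,250 = 0.0162, so the limits are the estimate x exp(±0.0317). With HR true = 0.70 and HR non-bleed = 1:

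| f | HR observed | 95% interval |
|---|---|---|
| 0.10 | 0.73 | 0.707 to 0.754 |
| 0.25 | 0.775 | 0.751 to 0.800 |
| 0.50 | 0.85 | 0.823 to 0.877 |

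Even at f = 0.10 the interval excludes 0.70.

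**5. Dependence on the non-bleed hazard ratio.** At f = 0.3 and HR true = 0.70, the observed HR is 0.79, 0.76, 0.70 or 0.64 when HR non-bleed is 1, 0.9, 0.7 or 0.5.

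**6. Power with the codes kept or removed, Optum, true HR 0.8, HR non-bleed 1.** With the codes kept, D = 1,354.77 and the diluted HR applies. With them removed, the remaining bleeds are D/(1 + HR observed) x (1 - f) x 1.8, analysed at HR 0.8.

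| f | Kept | Removed (events) |
|---|---|---|
| 0.1 | 0.955 | 0.972 (1,206) |
| 0.3 | 0.793 | 0.922 (918) |
| 0.5 | 0.492 | 0.807 (642) |

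Pooled power at true HR 0.8 is about 1.00 up to f = 0.5, with the codes kept or removed.

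**7. Baseline exclusion (section 5.3).** The bleeding-history step removes 2,721 + 3,332 + 23,500 = 29,553 patients.

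**The case against.** The strongest reply is that neither direction nor size is established. Movement toward 1 requires the non-bleed codes to have a hazard ratio nearer 1 than true bleeds. Step 5 shows no bias, or bias the other way, when that fails, and if the true HR is 1 and these codes are equal in both arms there is no bias at all. Unspecified anemia and some hemorrhoid or vaginal-disorder codes may mark real blood loss, which would lessen the dilution. The number of codes says nothing about the number of events. All of this stands, and it limits the claim to a conditional one.

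It is also fair that section 6.3.1 analyses major and CRNM bleeding separately, and that the major lists lack the anemia and coagulation codes and require transfusion at non-critical sites. That gives a cleaner secondary result but does not repair the primary composite.

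Four stronger readings are tempting, and the documents do not support them:

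- All 29,553 baseline removals are errors. That step uses both bleeding sheets and includes genuine bleeds; the number removed only by a non-bleed code is unknown.
- Precision should be judged on the 21,931 events in section 7 (2,226 + 2,570 + 17,135). Those are before matching; the planned comparison expects about 15,250.
- Abnormal coagulation results would be coded more often on one of the two drugs. Nothing in the documents addresses this.
- Every code in step 1 should simply be deleted. Some are ambiguous, and microscopic hematuria does name blood in the urine.

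**Conclusion.** The point stands in conditional form. As written, one inpatient code for a laboratory finding or a disease without stated bleeding is a primary-outcome event, so the outcome is less specific than the confirmed, adjudicated endpoint it emulates. If these codes occur about equally in both arms, or have a hazard ratio nearer 1 than true bleeds, the hazard ratio is diluted toward 1. The amount cannot be computed, because the documents give neither the share of events due to these codes nor arm-specific rates. The 0.73, 0.775 and 0.85 are illustrations that rest on assumed shares and a non-bleed HR of 1.

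In the pooled analysis the likely harm is bias rather than lost power: modest dilution could look like precise disagreement with the trial. In single databases power could suffer as well. Some patients without a bleed are also excluded at baseline, in unknown number. This should be settled before any comparative run.

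**What to change.** - Delete from both CRNM lists, and from the transfusion block of the major-bleeding lists where they appear: 285.9/D64.9, 790.92/R79.1, 530.1x/K20.x/K21.0, the perforation-only ulcer codes, 363.63/H31.32x, 455.6 and 455.9/K64.4. In step 1 this is 19 of the 24 ICD-9 codes and 20 of the 28 ICD-10 codes.
- Count the ambiguous codes only when a listed bleeding code is on the same admission: 455.1, 455.2, 455.4, 455.5, 455.7, 455.8 and the other K64.x; 593.81; 623.8/N89.8; microscopic hematuria R31.1/R31.2x.
- Use the same cleaned list for the Active Bleeding exclusion.
- Re-report event counts, not split by treatment, and power. Enter the present list in section 13.2 as a pre-specified sensitivity analysis.

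The cost is a code-list edit and a re-run of the feasibility counts. There will be fewer events, and some real bleeds coded only non-specifically will be lost. Pooled power at HR 0.8 stays near 1 even if half of comparator events are removed (about 7,224 events remain). Section 13 carries no date for the comparative run, so the change can still be made without knowledge of results.
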